## Background

In Europe, over 500,000 newborn infants are hospitalized each year. Infants are often separated from their parents during their hospitalization. One study showed that very preterm infants spent 80% of their time without any human contact (1). A European survey showed a large variation in parents' presence between hospitals, starting from 2.6 hours per day (unpublished data). Even when present, the parents are often just bystanders.(2,3) Separating the child from the parents places the socio-emotional and cognitive development at risk.(4,5) Studies have shown that parental involvement during hospitalization facilitates growth, socio-emotional, cognitive and linguistic development in preterm infants.(6-9)

An intervention directed at empowering parents shortened the length of stay by 3.9 days in preterm infants.(10) Vohr et al. showed that in settings with single-family room architecture, the infants of actively participating mothers had on average 15 days shorter length of stay compared to infants of non-active mothers. Interventions aimed at family-centered care are heterogeneous and their effects vary. In a meta-analysis comprising seven studies on family-centered care interventions, the length of stay was unaffected, but on the other hand e.g. preterm subpopulations were not considered.(11)

Parental presence can also be encouraged by hospital architecture. Even if modern hospitals nowadays include facilities also for parents based on the beneficial effects of single-family rooms (12,13), only 13.3% of 331 neonatal units provided parents with the facilities needed to stay with their infant throughout a 24-hour day.(14) Single-family rooms shortened the length of stay by 10 days among very preterm infants born before 30 gestational weeks in a randomized setting in Stockholm.(15) Also single-family room models are heterogeneous; according to a loose definition three solid walls suffices to qualify as single-family room, and does not necessarily include beds for the parents. A meta-analysis of 12 different single-family room studies did not show any significant benefit regarding length of stay compared to traditional hospital architecture.(16) However, in this meta-analysis most studies were observational studies without control groups; only one randomized study was included and no causal inferences could be drawn.

The Close Collaboration with Parents training program has been developed in Turku University Hospital, Finland. It is a structured and comprehensive training program for neonatal staff aiming to support parenthood and parental involvement in neonatal intensive care. The program addresses staff attitudes by reflection and exercises. The program has been shown to improve implementation of family-centered care in the varying contexts of neonatal intensive care units in both regional hospitals and university hospitals. After the completion of the training program, parents spent more time with their child during hospitalization.(17) Nurses reported that the training program strengthened the family-centered care culture and that the program enforced the role of the parents as primary caregivers.(18,19) Breast feeding was commenced on average three weeks earlier than before the training program, skin-to-skin care was commenced earlier and the amount of skin-to-skin care increased. The weight gain of premature infants improved by 44.5%, and the mothers of very preterm infants suffered from fewer depressive symptoms.(20,21)

It is imperative to study the economic impact of extensive, resource-demanding interventions that affect a whole neonatal unit. The Close Collaboration with Parents training program has so far been implemented in 11 neonatal units in Finland. In addition, four units have changed to single-family room architecture between 2014 and 2019. The national health care registers kept by the Institute for Health and Welfare contain a fully population-based dataset comprising all newborn infants (Medical Birth Register), hospitalizations and outpatient visits (Hospital

Discharge Register). These data are available since 1987, and enable retrospective research on the health and care of newborn infants. In Finland, we currently have a unique opportunity to study the effects of both a family-centered care intervention and single-family room architecture in more controlled circumstances than in previous studies: the interventions have been performed systematically throughout the country; societal support such as paid parental leave and universal access to health care grant all parents the same opportunities to participate; the register data are comparable for all units; and preterm infants can be studied as a separate group.

## **Research questions**

- Does the Close Collaboration with Parents training program affect the length of stay in neonatal units?
- Does single-family room architecture affect the length of stay in neonatal units?
- Do the interventions affect the need for outpatient visits after discharge during the first year of life?
- Are the interventions cost-effective?
- Do the interventions affect early postnatal growth in preterm infants?

[figure not shown]
Our hypotheses are that the length of stay will be shorter, outpatient visits fewer and early postnatal growth better in units where either or both of these interventions have been implemented.

## **Methods**

The study population will consist of all newborn infants born from January 1st 2006 to December 31st 2020, who have needed care in a neonatal unit immediately after birth. These infants will be identified from the Hospital Discharge Register. Data on vital background data, birth details, diagnoses, length of stay, growth parameters and outpatient visits will be obtained from the Hospital Discharge Register and the Medical Birth Register. These data will be linked through the infants' personal identification codes, which will be replaced by a pseudonymized ID-number before delivering the data to the research group. Planned subgroup analyses will be done for preterm infants and for infants with significant congenital anomalies.

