### Outcomes:

The *primary* outcome is the length of stay during the initial hospitalization to neonatal care. Comparisons will be made between infants cared for in intervention units and those cared for in non-intervention units.

*Secondary* outcomes are:

Corrected gestational age at discharge

The amount of outpatient visits after discharge during the first year of life

Growth parameters (weight, length, head circumference) at discharge compared to national standards

Change in growth parameters from birth to discharge

Cost effectiveness (according to hospitalization cost analyses carried out by the Institute for Health and Welfare)

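### Only infants admitted to a neonatal unit enter the cohort, so an unmonitored change in mild admissions after adoption could be read as a change in length of stay

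*Combined protocol and SAP*

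**What the plan says.** The Methods section of the combined protocol and SAP takes as its population all newborns of 2006 to 2020 "who have needed care in a neonatal unit immediately after birth. These infants will be identified from the Hospital Discharge Register". It sets no limit on gestational age, severity or minimum stay. Under Outcomes, the primary "outcome is the length of stay during the initial hospitalization to neonatal care", and "Comparisons will be made between infants cared for in intervention units and those cared for in non-intervention units".

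The Background describes "extensive, resource-demanding interventions that affect a whole neonatal unit". Of the training it says: "The program addresses staff attitudes by reflection and exercises". On architecture it says that "four units have changed to single-family room architecture between 2014 and 2019".

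Three parts of the plan bear on case mix. The mixed model under Statistical analysis is meant to account for unit, degree of prematurity and intervention. Neonatal morbidities are among the further covariates that may be included. Methods plans a subgroup analysis of preterm infants.

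No section plans an admission rate, a live-birth denominator or a check on the mix of admitted infants over time. The source for such a denominator is already in use: the Background says the national registers "contain a fully population-based dataset comprising all newborn infants (Medical Birth Register), hospitalizations and outpatient visits (Hospital" (the sentence goes on to complete the name of the Hospital Discharge Register), and Methods links the two.

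**The concern.** For an infant born after adoption, entry to the cohort follows exposure. A very preterm infant will presumably be admitted whatever the unit's culture or layout. For a mildly ill late preterm or term infant, admission may be a matter of judgement. A unit that has been trained to keep parents and infant together might leave such an infant with the mother outside the unit. A unit with family rooms might admit that infant more readily.

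Either change alters the mix of stays being averaged. Fewer mild admissions lengthen mean stay, which can hide a benefit while total unit-days fall. More mild admissions shorten it, which imitates the effect hypothesised under Research questions while unit-days rise. The plan asks whether the interventions are cost-effective, and its closing section on implications points to resource allocation, so the distinction matters. Corrected age at discharge, growth at discharge and outpatient visits are measured in the same selected infants.

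**Working it through.** The documents give no mean stay, admission rate, effect size or standard deviation, so there is no figure of the plan's own to reproduce. Every numerical input below is an assumption, and the true effect on each infant's stay is set to zero. Any change in the mean is therefore artefact.

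**Step 1: simple mixture.** Assume a mean stay of 10 days. If a share f of all admissions, with stay s, is avoided, the mean becomes (10 − f·s)/(1 − f). If the same share is added, it becomes (10 + f·s)/(1 + f). With s = 3 days:

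| f | avoided | added |
|---|---|---|
| 5% | 9.85/0.95 = 10.37 | 10.15/1.05 = 9.67 |
| 10% | 9.70/0.90 = 10.78 | 10.30/1.10 = 9.36 |
| 20% | 9.40/0.80 = 11.75 | 10.60/1.20 = 8.83 |

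At f = 10% with s between 2 and 4 days, the mean runs from 10.67 to 10.89 (avoided) or from 9.27 to 9.45 (added). The numerators show total days moving the opposite way from the mean.

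**Step 2: allow for gestational age, as the plan's model intends.** Assumed baseline admissions:

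| Stratum | share | mild share | stay, mild / other (days) | mean stay |
|---|---|---|---|---|
| Very preterm | 12% | 0% | 45 / 45 | 45.0 |
| Moderate and late preterm | 38% | 30% | 5 / 14 | 0.3×5 + 0.7×14 = 11.3 |
| Term | 50% | 60% | 2 / 6 | 0.6×2 + 0.4×6 = 3.6 |

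Overall mean: 0.12×45 + 0.38×11.3 + 0.50×3.6 = 11.49 days.

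Now let mild admissions fall by 20%.

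- Very preterm: unchanged, difference 0.00.
- Moderate and late preterm: (0.24×5 + 0.7×14)/0.94 = 11.70, difference +0.40.
- Term: (0.48×2 + 0.4×6)/0.88 = 3.82, difference +0.22.
- Crude: (5.40 + 4.18 + 1.68)/(0.12 + 0.3572 + 0.44) = 11.26/0.9172 = 12.28, difference +0.78.
- Adjusted for stratum by least squares, where each stratum is weighted by n₀n₁/(n₀ + n₁), giving 0.060, 0.184 and 0.234: (0.184×0.40 + 0.234×0.22)/0.478 = +0.26.

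Unit-days per baseline admission fall from 11.49 to 11.26, or 2.0%, while the crude mean rises by 0.78/11.49 = 6.8%.

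**Step 3: other shifts, same inputs.**

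| Change in mild admissions | crude (days) | adjusted (days) | very preterm (days) |
|---|---|---|---|
| −30% | +1.23 | +0.41 | 0.00 |
| −20% | +0.78 | +0.26 | 0.00 |
| +20% | −0.66 | −0.22 | 0.00 |
| +30% | −0.96 | −0.32 | 0.00 |

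About one third of the crude artefact survives gestational-age adjustment (0.26/0.78 = 0.33). The rest of it comes from the changed balance of strata, which the adjustment handles.

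**The case against.** The mechanism is not documented. Every programme effect that the Background reports occurs after admission: parents' time with the infant, breastfeeding, skin-to-skin care, weight gain and maternal mood. Nothing says who decides on admission or that admissions moved. That is correct, and it limits the point to a risk.

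The planned safeguards are real. Degree of prematurity is a stated purpose of the model, morbidity bears directly on severity, and the preterm subgroup overlaps with part of the remedy. They still leave gaps. Morbidity is only a candidate covariate, and its diagnoses are recorded in infants already selected. The preterm subgroup includes moderate and late preterm infants, for whom admission may be discretionary. A unit effect absorbs a stable admission threshold but not one that changes at adoption.

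The research question concerns stay in neonatal units, which exists only for admitted infants. That also stands. Unit-days per live birth answers a different question, and a narrower headline population would be a trade-off, so neither should replace the primary outcome.

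A reader might infer two stronger things. One is that the primary estimate will have the wrong sign. The documents do not support this: the illustration sets the true effect to zero, and a true effect larger than the residual artefact would keep its sign. The other is that the cost analysis leaves out avoided or added admissions. The plan says only that it will follow hospitalisation cost analyses by the Institute for Health and Welfare and does not describe the method, so the point cannot be settled from the text.

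**Conclusion.** The concern holds as an unaddressed risk of selection after exposure, not as a demonstrated bias. The structure is plain in Methods, Outcomes and Background: admission defines the cohort, the interventions are unit-wide, and no analysis of admissions is planned. Whether admissions changed, and in which direction, is unknown.

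Under the assumed inputs, a 20% shift in mild admissions gives about 0.7 to 0.8 day crude and 0.2 to 0.3 day after gestational-age adjustment, with none in a stratum where all infants are admitted. Good morbidity adjustment could shrink this further.

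For scale, the Background cites differences of 3.9 days (preterm infants), 10 days (very preterm infants) and 15 days (by mothers' participation, gestational age not given). The artefact is small beside these, but none of them is an effect in the whole admitted population, where stays are shorter and the plan names no expected effect.

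**What to change.** Keep length of stay among admitted infants as the primary outcome and add three analyses.

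(a) The admission rate per live birth by gestational-age stratum, birth hospital and period, with the change at adoption compared with the change in control units. The comparison is needed because background drift over 2006 to 2020 would otherwise be mistaken for an effect of adoption.

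(b) Neonatal-unit days per live birth, counting 0 for infants not admitted, as a supporting analysis for the resource and cost questions. The denominator comes from the Medical Birth Register.

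(c) A sensitivity analysis of length of stay in the gestational-age band where admission before adoption was near universal, with the cut set from those pre-adoption data.

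State in advance how they will be used: if admission rates changed relative to control units, report the all-admitted estimate with that caveat and rely on (b) and (c). A stable rate is reassuring but does not exclude offsetting changes in mix.

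The cost is a little more analysis. Since the Timeline says a data permit was applied for in 2020, it may also need extending to live-birth counts by hospital, period and gestational age; (a), (b) and the cut in (c) all depend on those counts.

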### **Description of the interventions: Two interventions are studied (Figure 1)**

- Close Collaboration with Parents-training program in 11 neonatal units
- Adoption of single-family room architecture in 4 neonatal units
- Control group: Infants cared for in the 10 neonatal units where neither of the interventions have been implemented.

### Outcomes:

The *primary* outcome is the length of stay during the initial hospitalization to neonatal care. Comparisons will be made between infants cared for in intervention units and those cared for in non-intervention units.

*Secondary* outcomes are:

Corrected gestational age at discharge

The amount of outpatient visits after discharge during the first year of life

Growth parameters (weight, length, head circumference) at discharge compared to national standards

Change in growth parameters from birth to discharge

Cost effectiveness (according to hospitalization cost analyses carried out by the Institute for Health and Welfare)

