### Statistical analysis:

The planned analyses include a linear mixed model-approach to account for the effect of unit, degree of prematurity and intervention. Variables that will be considered for inclusion into the model are gestational age at birth, mode of delivery, birth weight z-score, plurality, neonatal morbidities, and receipt of antenatal steroids.

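### The plan names no unit-level covariate, does not define the unit effect and does not date exposure, so confounding by level of care is not shown to be controlled

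*Combined protocol and SAP*

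**What the plan says.** The Outcomes section states the primary contrast: "Comparisons will be made between infants cared for in intervention units and those cared for in non-intervention units". Description of the interventions gives the groups: "Close Collaboration with Parents-training program in 11 neonatal units", "Adoption of single-family room architecture in 4 neonatal units", and a control group of "Infants cared for in the 10 neonatal units where neither of the interventions have been implemented". Controls are therefore units that never had either intervention. The plan does not say how infants born in an intervention unit before its implementation date are counted.

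Statistical analysis proposes "a linear mixed model-approach to account for the effect of unit, degree of prematurity and intervention". The candidate covariates, which are to be considered rather than fixed in advance, are "gestational age at birth, mode of delivery, birth weight z-score, plurality, neonatal morbidities, and receipt of antenatal steroids". No unit characteristic is listed and calendar year does not appear. The subgroups planned under Methods are preterm infants and infants with significant anomalies; none is by level of care.

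On hospital type, the Background says only that the training program was put in place in "varying contexts of neonatal intensive care units in both regional hospitals and university hospitals". This describes units that ran the training. The split by arm is not in the readable text, and Figure 1 is not shown.

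**The concern.** The intervention is a property of the unit and was not allocated at random. University and regional units may differ in discharge and transfer practice, and in how these changed over the 15 birth years. Infant-level covariates adjust for part of the case mix but not for unit practice. If hospital type is unevenly spread across the arms, part of the difference in stay between hospital types would be credited to, or subtracted from, the training program or the rooms. The results are meant to inform resource allocation, so the source of any difference matters. The room contrast is the most exposed because it rests on four units.

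**Working it through.** The plan gives no effect size, power or precision figure, so there is none to reproduce. The check has five steps.

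**1. Level of each covariate.** Gestational age, mode of delivery, birth weight z-score, plurality, neonatal morbidities and antenatal steroids: six of six vary by infant or pregnancy, none by unit.

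**2. What the unit term can do.**
- Ever/never label, unit fixed: the label is a sum of unit indicators, so the intervention effect cannot be estimated.
- Ever/never label, unit random: the effect can be estimated, but a hospital-type imbalance stays in the coefficient.
- Exposure dated within units, with unit effects and calendar year: a stable hospital-type difference is largely removed.

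The plan does not say which applies. The wording under Outcomes is closest to the second.

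**3. Size of the bias in an ever/never contrast.** Bias = D × (pI − pC), where D is the adjusted university-minus-regional difference in stay, and pI and pC are the university shares among intervention and control units. All values below are assumptions. A positive sign means the intervention looks worse than it is.

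| pI vs pC | D = 1 day | D = 2 days | D = 4 days |
|---|---|---|---|
| equal | 0 | 0 | 0 |
| 0.33 vs 0.10 | 0.23 | 0.46 | 0.92 |
| 0.10 vs 0.33 | −0.23 | −0.46 | −0.92 |
| 0.75 vs 0.10 (extreme room case) | 0.65 | 1.3 | 2.6 |

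For scale, the Background cites a 3.9-day reduction from a parent-empowerment intervention in preterm infants: 0.46/3.9 = 12% and 1.3/3.9 = 33%.

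**4. Simulation, true effect zero.** Assumptions: 11 trained and 10 control units, births 2006–2020, 30 infants per unit-year, implementation between 2010 and 2018, unit SD 1 day, residual SD 10 days, the same calendar trend in all units, 60 replicates. Entries are mean bias in days; simulation standard errors were 0.04–0.07.

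| University units, trained / control; D | Formula | Random unit, ever/never | Same, plus level of care | Random unit, dated | Fixed unit and year, dated |
|---|---|---|---|---|---|
| 4/11 and 1/10; D = 3 | 0.79 | 0.81 | 0.02 | 0.16 | 0.08 |
| 4/11 and 1/10; D = 5 | 1.32 | 1.38 | 0.07 | 0.09 | 0.01 |
| 2/11 and 2/10; D = 3 | −0.05 | −0.13 | −0.08 | −0.01 | 0.01 |

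The simulation agrees with the formula. Either level of care or dated exposure removes most of the bias. The dated columns do not test differing trends by hospital type, because none was simulated. By arithmetic, in any unit that switches once within the 15 birth years, the midpoints of its before and after periods lie 15/2 = 7.5 years apart. If trends by hospital type differed by an assumed 0.1 day per year with a 65-point imbalance, 0.1 × 7.5 × 0.65 = 0.49 day would remain.

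**5. Precision cost of adjusting.** With equal unit weights and groups that do not overlap, the variance of a between-unit contrast, in units of the between-unit variance, is 1/nI + 1/nC + (pI − pC)²/W, where W sums n·p·(1 − p) over the groups in the model.
- Rooms, unadjusted: 1/4 + 1/10 = 0.35.
- Rooms (3/4) and controls (1/10), adjusted: W = 0.75 + 0.90 = 1.65; 0.35 + 0.4225/1.65 = 0.61; √(0.61/0.35) = 1.32, so intervals about 32% wider.
- Trained units (4/11 university, assumed) in the same model: W = 1.65 + 2.55 = 4.20; 0.35 + 0.4225/4.20 = 0.45; about 13% wider.
- Equal shares: the added term is zero.

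Lost degrees of freedom and trend terms are not included.

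**The case against.** The strongest objection is that no imbalance is shown. The Background sentence on hospital types concerns units that ran the training and says nothing about control or room units. A reader might infer that level of care is in fact confounded with the interventions, or that one or two university hospitals determine the room result. The documents support neither. They do not give hospital type by arm, and nothing in the readable text says that any room unit is in a university hospital. This objection stands, and it is why the point is conditional and every figure in days is an illustration.

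Second, the model does contain a unit effect, and the data would allow a dated analysis: births run from 2006 to 2020 and the room changes fell between 2014 and 2019. With exposure dated within units, a stable hospital-type difference largely cancels. That is correct, and the fix uses it. But the plan does not state such a contrast, so its protection cannot be assumed, and differing trends would remain.

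Third, gestational age, birth weight z-score, morbidities and antenatal steroids already handle part of the severity difference. This is true for case mix, but not for discharge or transfer practice.

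Fourth, the unit count is uncertain. Adding the groups gives 11 + 4 + 10 = 25, but the hypothesis under Research questions allows a unit to have both interventions. So 25 is an upper bound, and intervention units cannot be assumed to fall into two separate groups.

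**Conclusion.** The concern holds in conditional form. The primary contrast is between non-randomised units, no unit-level covariate is named, and neither the form of the unit effect nor the timing of exposure is specified. The plan therefore does not show that level of care is controlled.

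Its size cannot be read from the documents. It is zero if hospital type is balanced across arms and may have either sign if it is not. About 0.5 day in absolute value rests on an assumed 2-day difference and a 23-point imbalance. The 1.3 days for rooms needs a strong imbalance (3 of 4 against 1 of 10) that the documents neither state nor exclude. The root gap is the unspecified unit effect and exposure date; confounding by level of care is one consequence of it.

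**What to change.** Amend Statistical analysis as follows.

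1. Classify each infant as exposed or unexposed by birth date relative to the unit's implementation date, separately for each intervention. Include unit effects and calendar year, and state whether unit is fixed or random. Earlier births in intervention units then serve as within-unit controls; for all four room units, 2006–2013 precedes any conversion.
2. Prespecify level of care (university or regional). If unit is random, enter it as a unit-level covariate. If unit is fixed, enter only its interaction with birth period, because the main effect is collinear with the unit terms.
3. Report the number of university and regional units in each arm, and adjusted length of stay before implementation by group and level, as a check that the groups were not already diverging.
4. Where a level of care has no control unit, say so, and state that the contrast there rests on within-unit change only.

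This changes the analysis plan and needs only the unit's hospital type and implementation date as additional inputs. The price is precision: negligible if hospital type is balanced, but possibly 10–30% wider intervals for the four-unit room contrast if it is strongly imbalanced. That range comes from the between-unit calculation above and depends on its assumed shares.

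### The plan asks about staff training and single-family rooms separately, but states only one undivided contrast and one uncoded intervention term, so it does not say how the two effects will be told apart

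*Combined protocol and SAP*

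**What the plan says.** The Research questions section puts two distinct questions on the primary outcome: "Does the Close Collaboration with Parents training program affect the length of stay in neonatal units" and "Does single-family room architecture affect the length of stay in neonatal units". Its hypothesis concerns outcomes "in units where either or both of these interventions have been implemented", so units with both are foreseen.

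The Description of the interventions lists the two separately, with "Close Collaboration with Parents-training program in 11 neonatal units" and rooms in 4 units. It gives a single comparator: "Control group: Infants cared for in the 10 neonatal units where neither of the interventions have been implemented".

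Under Outcomes, the only contrast stated for length of stay is: "Comparisons will be made between infants cared for in intervention units and those cared for in non-intervention units".

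The Statistical analysis section plans "a linear mixed model-approach to account for the effect of unit, degree of prematurity and intervention". It does not say whether intervention is one yes/no variable, two indicators or a factor with several levels.

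The readable text does not say how many units had both, how those units are classified, or which estimate answers which question. Figure 1, cited in the Description of the interventions, is not shown in the text available for review.

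**The concern.** Two questions need two estimates, and the plan describes one comparison. There are two natural ways to carry out what is written, and each has a different problem.

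- **Pooled.** All units with any intervention are compared with the 10 units that had none. This gives one number, a weighted mix of the two effects. The problem does not depend on overlap.
- **Each against neither.** The 11 training units and the 4 room units are each compared with the same 10 controls. A unit with both then sits in both exposed groups, so the other intervention is an unbalanced co-intervention. This problem exists only if some units had both.

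The section on meaning and implications says that the results should inform how resources are allocated, and cost-effectiveness is a secondary outcome. Training staff and rebuilding a unit are different investments. A blended or cross-credited estimate would not show which of them accounts for any days saved.

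**Working it through.** The plan gives no effect size, power or sample-size figure, so there is none to reproduce. The check is arithmetic at unit level.

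**Inputs from the documents.** There are 11 training units, 4 room units and 10 units with neither (Description of the interventions).

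**Assumptions.** Units weigh equally, effects add, and in a unit with both, the two exposures overlap in time. Let T be the days saved by training, S the days saved by rooms, and k the number of units with both. The documents do not give k in readable form; it can lie between 0 and 4. There are then 15 − k intervention units.

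**Formulas.**
- Pooled against neither: (11T + 4S)/(15 − k)
- Rooms against neither: S + (k/4)T
- Training against neither: T + (k/11)S

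**Pooled reading with no overlap (k = 0).**
- T = 2, S = 0 (assumed): (11 × 2 + 4 × 0)/15 = 1.47 days. Neither true effect is 1.47.
- T = 0, S = 10: (11 × 0 + 4 × 10)/15 = 2.67 days. Neither true effect is 2.67.

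**Each-against-neither reading.** The last three columns use T = 3.9 and S = 10. Both figures appear in the Background, for a parent-empowerment programme in preterm infants and for single-family rooms in infants born before 30 weeks. They serve only as illustration and are not predictions for this study.

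| k | Intervention units | Share of T in room estimate (k/4) | Share of S in training estimate (k/11) | Rooms v neither, days | Training v neither, days | Pooled, days |
|---|---|---|---|---|---|---|
| 0 | 15 | 0% | 0% | 10.0 | 3.90 | 5.53 |
| 1 | 14 | 25% | 9% | 10.975 | 4.81 | 5.92 |
| 2 | 13 | 50% | 18% | 11.95 | 5.72 | 6.38 |
| 3 | 12 | 75% | 27% | 12.925 | 6.63 | 6.91 |
| 4 | 11 | 100% | 36% | 13.9 | 7.54 | 7.54 |

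If rooms did nothing and training saved 2 days, rooms against neither would show 2k/4 days: 0, 0.5, 1.0, 1.5 or 2.0 for k = 0 to 4, none of it due to rooms.

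**Two indicators entered together.** A least-squares fit to the same unit-level values, with one indicator for training and one for rooms and all units kept, returned 3.9 and 10.0 for every k from 0 to 4. At k = 4 no unit has rooms alone. Both main effects can still be estimated if effects add, but an interaction cannot be estimated from differences between units.

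**The case against.** The strongest reply is that this is a gap in detail and not a wrong method. The sentence under Outcomes is generic and does not say that the interventions will be merged. The Description of the interventions lists them separately, and the intervention term could be coded as two indicators without departing from the text. Naming a control group does not exclude other units from the model. All of this stands. A reader might infer that the plan commits itself to pooling, and the documents do not go that far. Even so, wording that permits a suitable coding does not specify one, and the only contrast actually written down is undivided.

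A reader might also infer that each effect will necessarily be credited with the other's. The documents do not support this either, for four reasons:
- A pooled contrast produces one blended number, so it does not cross-credit two.
- Cross-crediting needs k above 0. The hypothesis allows for units with both but gives no count, Figure 1 may show it, and the Background introduces the four room units as additional to the training units, which can be read as no overlap.
- Exposure was not fixed. Births run from 2006 to 2020 and the change to rooms took place between 2014 and 2019, so k/4 and k/11 are upper limits that apply when the exposures coincide.
- The direction of the error assumes that the other intervention shortens stay. The Background cites meta-analyses that found no effect on length of stay for either type of intervention.

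Finally, the plan speaks of resource allocation in general. It does not present the study as a choice between training and building, so it cannot be said that the wrong one would be credited.

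**Conclusion.** The point holds in a conditional form. The plan asks two questions, foresees units with both, and states one contrast, one comparator and one uncoded intervention term. Nothing in the readable text separates the effects.

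If the contrast is pooled, it answers neither question unless the two effects happen to be equal and no unit has both. This failure needs no overlap. If each intervention is compared with neither, the room estimate can take in between 0 and 100% of the training effect, and the training estimate between 0 and 36% of the room effect, as k runs from 0 to 4. These shares rest on equal unit weights, additive effects and exposures that coincide in time. The sizes in days are illustrative, since the effects are assumed.

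Because the gap lies in the sole stated contrast for the primary outcome, and a better analysis is available at little cost, it should be closed before the data are analysed.

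**What to change.** In Outcomes and Statistical analysis, replace the single contrast with two indicators entered together in the mixed model: training in place and single-family rooms in place.

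- Code each by the unit's status at the infant's birth or admission, because exposure changed within units during 2006–2020. This also avoids indicators that are constant within a unit, which could not be estimated if the unit effect is fixed.
- Keep all units in the model. Trained units without rooms then inform the room effect, and room units without training, if there are any, inform the training effect.
- State the number of units with both, and name the coefficient that answers each research question.
- Report a training-by-room interaction only as exploratory, and only if it can be estimated.
- Report any pooled any-intervention estimate as descriptive only.

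**Cost.** A change of wording and of model terms, with no new infant data. The coding does need each unit's implementation dates. It also brings before-and-after information into the estimates, so the model will need a calendar-time term, which the present list of candidate variables lacks. The main statistical price is a wider interval for the room effect. With 4 room units, that width reflects real uncertainty.
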